#### **4.2.2 Rationale for Dose Selection/Regimen/Modification: CMP-001**

During the peri-operative period (Prime Phase), CMP-001 5mg will be administered subcutaneously for the first dose (week 1). Thereafter, CMP-001 will be administered intra-tumorally at 10mg weekly (weeks 2-7).

During the post-surgical period (Boost Phase), CMP-001 5mg weekly will be administered subcutaneously every 4 weeks for up to 54 weeks.

Upon initial exposure to CMP-001, antibodies against the Q-beta capsid protein are formed. Thereafter the FC portion of the antibody bind to the FCR- $\gamma$  on the pDC. These antibodies are necessary to facilitate the binding of the VLP to the FC. After the first dose approximately 100% of the subjects exposed to CMP-001 demonstrate the presence of these antibodies. Therefore, to maximize the therapeutic potential of CMP-001 and minimize the number of intratumoral injections, the first dose of CMP-001 will be administered subcutaneously.

The rationale for the weekly schedule is primarily based upon the safety and efficacy results from the ongoing study in metastatic melanoma noted above. A comparison of the weekly and Q3weekly schedule in that study demonstrated a trend towards improved efficacy in the weekly schedule. During the initial safety run-in of this study, a variety of doses were explored based on tumor size. The rationale for the fixed dose during Prime Phase weeks 2-7 is based on the safety and efficacy results from the initial safety run-in that showed no increased incidence of adverse events in patients treated with higher doses of CMP-001.

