## **5.2.2 CMP-001 Dose Selection/Modification**

During the Prime Phase, the first dose of CMP-001 (week 1) is fixed at 5mg subcutaneously. Subsequent doses of CMP-001 administered during the Prime Phase (weeks 2-7) will be at 10mg administered intra-tumorally. Should patients develop side effects, intra-tumoral doses during this period of the Prime Phase (weeks 2-7) may be reduced (see **Table 5.2.2.3-1**).

Following resection, during the Boost Phase, the CMP-001 dose is fixed at 5mg injected subcutaneously at the site of the resected tumor.

Rationale for dose selection is provided in **Section 4.2.2 – Rationale for Dose Selection/Regimen/Modification: CMP-001**.

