**Table 5.2.2.3-1: CMP-001 Injection Volume Guidelines Based on Tumor Size (Doses 2-6 in Prime Phase)**

Dose Level	CMP-001 Dose (6mg/mL concentration)	Total Volume Injected
1	10mg	~2.0 mL
-1	7.5mg	~1.5 mL
-2	5mg	~1.0 mL
-3	2.5mg	~0.5 mL

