#### **5.2.2.4    CMP-001 Dose Modification**

CMP-001 will be dose-reduced in patients who develop CMP-001 related DLT and resume study therapy with Nivolumab/CMP-001 combination if Investigator determines that continued treatment with CMP-001 is in the subject's best interest. In this event, CMP-001 will be dose reduced as in **Table 5.2.2.3-1**.

[figure not shown]
CMP-001 will be withheld for CMP-001 related Grade 4 hematologic toxicities, non-hematological toxicity  $\geq$  Grade 3 including laboratory abnormalities, and severe or life-threatening AEs.

If CMP-001 is permanently discontinued for, subjects may continue to receive Nivolumab.

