#### 5.2.2.7 Management of CMP-001 toxicity

##### CMP-001 Associated Adverse Events

If subjects develop inflammation at the injection site this may be managed using cold compresses and/or acetaminophen or non-steroidal anti-inflammatory agents. If flu-like symptoms (i.e., fever, myalgia, and headache) arise, these may be managed using acetaminophen or non-steroidal anti-inflammatory agents.

[figure not shown]
It is expected that symptoms associated with a large release in cytokines at the time of injection could present 1-4 hours after the injection. These symptoms could include: fever, nausea/vomiting, chills/rigors, and hypotension. Subjects must remain in observation until all of these symptoms have resolved to  $\leq$  Grade 1. Refer to **Table 4.1.4-1** for current CMP-001 safety profile in the ongoing CMP-001-001 clinical study.

Subjects who experience a DLT will have dosing of CMP-001 withheld until the toxicity has returned to  $\leq$  Grade 1. If the Investigator determines that continued treatment with CMP-001 is in the subject's best interest, treatment may resume at a reduced dose of CMP-001. Only one dose reduction is allowed. Subjects who still experience DLTs at Dose Level-1 must come off study.

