### 8.2 Safety Monitoring

The PD-1/CMP-001 combination has been tested in the PD-1 refractory setting in melanoma including in a phase I study that evaluated multiple doses of CMP-001 including 5mg, 7.5mg and 10mg. The safety profile observed thus far suggests that the **risk of additive toxicities are unlikely to be significantly increased** in the neoadjuvant setting. Further, the dose being tested in this study (5mg) is 50% the ceiling dose tested in other CMP-001 studies in combination with PD-1 inhibitors, none of which reported a toxicity rate >33%.

However, in the context of this neoadjuvant trial, we will monitor dose limiting toxicities (DLTs) for 4 weeks for the 1st 3 patients accrued. DLT is defined as any adverse event(s) (AEs) considered possibly, probably, or definitely related to the CMP-001 plus nivolumab regimen, which occur during the first 15 days of therapy (i.e. following 3 doses of CMP-001; W1D1, W2D1, W3D1) IN the Prime phase only. Attribution of AEs specifically to either CMP-001 or nivolumab is challenging, therefore, the relationship to CMP-001 should be based on attribution to the combination of the two drugs. During DLT monitoring period, no further accrual will be permitted. Any patient who has started the studied treatment will be evaluable for safety.

The following AEs will be considered DLTs if deemed related to study therapy:

- Hematologic
  - Grade 4 neutropenia
  - Febrile neutropenia, defined as absolute neutrophil count (ANC)  $\leq 1000/\text{mm}^3$  with a temperature of  $\geq 38.3$  degrees °C
  - Grade  $\geq 3$  neutropenic infection
  - Grade  $\geq 3$  thrombocytopenia with bleeding
  - Grade 4 thrombocytopenia
- Non-hematologic
  - Grade  $\geq 3$  toxicities (non-laboratory)
  - Grade  $\geq 3$  nausea, vomiting or diarrhea despite maximal medical intervention
  - Grade 4 aspartate aminotransferase (AST) and alanine aminotransferase (ALT)

- Other (non AST/ALT) non-hematologic Grade  $\geq 3$  laboratory value if the abnormality leads to overnight hospitalization

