IMPORTANT: CMP-001 is designed to specifically bind to Toll like receptor 9 (TLR9) which is expressed in the endosomes of pDCs. Upon activation through TLR9, pDCs will secrete large amounts of type 1 interferons and associated Th1-promoting cytokines. Given this mechanism of action, it is expected that the adverse event profile associated with intratumoral injection of CMP-001 may be similar to that seen after administration of interferons (e.g. flu-like symptoms such as fever, rigors, nausea & vomiting). In addition, given the release of IFN-inducible chemokines and cytokines, symptoms associated with cytokine release, such as chills/rigors, fever, nausea/vomiting and hypotension, may occur within hours of a CMP-001 intratumoral injection. Recommended prophylaxis, outlined above in **Section 5.2.2.1.** may help to minimize the severity of these reactions.

An AE believed to be caused by tumor flare or pseudoprogression does not necessarily need to be considered a DLT. Any such cases that would otherwise meet DLT criteria must be discussed immediately with the Principle Investigator. If the Principle Investigator and Sponsor agree that tumor flare is a likely explanation for the AE, treatment with CMP-001 may continue so long as the subject is closely monitored by the Principle Investigator or study staff while on study.

Subjects who experience a DLT will have CMP-001 and nivolumab dosing withheld until the toxicity has returned to  $\leq$  Grade 1. If the Investigator determines that continued treatment with CMP-001 is in the subject's best interest, treatment may resume at a reduced dose (2.5mg weekly or every 4 weeks; 1 dose level lower) at the same schedule after consultation with the Principle Investigator. If a CMP-001 injection is delayed due to toxicity it should be given as soon as possible once the toxicity has resolved. If a subject experiences DLT on a reduced dose of CMP-001, further accrual will be halted.

Subjects may remain on the same dose of nivolumab. Any dose modification should follow the approved nivolumab label.

The Investigator may escalate the subject back to the original CMP-001 dose level if: 1) the lower dose level was tolerated without any DLTs; 2) Sponsor approval is given.

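### Section 8.2 resumes CMP-001 at 2.5 mg after a DLT, a rule written for a 5 mg regimen; after a 10 mg intra-tumoral dose, section 5.2.2.4 and Table 5.2.2.3-1 give 7.5 mg

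*Combined protocol and SAP*

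**What the plan says.** Two parts of the protocol set the CMP-001 dose after a DLT.

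**Section 8.2, Safety Monitoring.** It describes the regimen thus: "the dose being tested in this study (5mg) is 50% the ceiling dose tested in other CMP-001 studies". For a subject who has had a DLT and recovered, it says that "treatment may resume at a reduced dose (2.5mg weekly or every 4 weeks; 1 dose level lower) at the same schedule", after consultation with the Principal Investigator. It halts further accrual if a DLT occurs on a reduced dose. It allows return to the original level if the lower level was tolerated without a DLT and the Sponsor approves.

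**Sections 4.2.2 and 5.2.2 to 5.2.2.7.** The first dose is 5 mg subcutaneously. After that, section 4.2.2 states "CMP-001 will be administered intra-tumorally at 10mg weekly (weeks 2-7". Section 5.2.2 says that "intra-tumoral doses during this period of the Prime Phase (weeks 2-7) may be reduced" if side effects develop, and points to Table 5.2.2.3-1. That table is headed "Doses 2-6 in Prime Phase" and lists 10 mg (Level 1), 7.5 mg (Level -1), 5 mg (Level -2) and 2.5 mg (Level -3). For a subject who resumes after a CMP-001 related DLT, section 5.2.2.4 says "In this event, CMP-001 will be dose reduced as in" that same table. Section 5.2.2.7 adds: "Only one dose reduction is allowed. Subjects who still experience DLTs at Dose Level-1 must come off study".

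**The concern.** Section 8.2 and section 5.2.2.4 both tell staff what to give after a DLT, and for a 10 mg injection they give different answers. Within 8.2 the number and its label also disagree once the starting dose is 10 mg, because 2.5 mg is not one level lower on the protocol's only dose-level table.

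This instruction is used immediately after a serious toxicity, with an agent that section 5.2.2.7 links to severe hypotension. Staff working from section 8 and staff working from section 5 would give different doses to the same patient.

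There is also a trial-level consequence. A subject resumed at 7.5 mg under section 5 who has another DLT must come off study under 5.2.2.7. Whether that event also stops accrual depends on whether 7.5 mg counts as the reduced dose meant in 8.2, where the only figure given is 2.5 mg.

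Finally, the reassurance in 8.2 that the study dose is half the ceiling does not describe weeks 2-7.

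**Working it through.** No sample-size or error-rate figure is involved. The check is a look-up in Table 5.2.2.3-1 and simple arithmetic.

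**Inputs**
- Study dose according to 8.2: 5 mg, stated as 50% of the ceiling.
- Resumption dose in 8.2: 2.5 mg, stated as one level lower.
- Current Prime doses (4.2.2, 5.2.2): week 1, 5 mg subcutaneous; weeks 2-7, 10 mg intra-tumoral.
- Dose levels (Table 5.2.2.3-1): 10, 7.5, 5 and 2.5 mg.
- DLT window (8.2): the first 15 days, covering W1D1, W2D1 and W3D1.

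**Step 1: reproduce 8.2 on its own terms.** Implied ceiling = 5 / 0.50 = 10 mg. From 5 mg, the next level down in the table is 2.5 mg. So 8.2 is coherent if the study dose is 5 mg.

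**Step 2: apply it to the current regimen.** The weeks 2-7 dose is 10 / 10 = 100% of the implied ceiling, not 50%. From 10 mg, one level down is 7.5 mg. Reaching 2.5 mg takes three steps (10 to 7.5 to 5 to 2.5).

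**Step 3: size of the difference per injection**
- 8.2: (10 - 2.5) / 10 = 75% reduction.
- Table: (10 - 7.5) / 10 = 25% reduction.
- Ratio of the two doses: 7.5 / 2.5 = 3.

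**Step 4: remaining Prime intra-tumoral total, if no dose is missed or re-escalated**

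| DLT after | Doses left | Under 8.2 | Under the table |
|---|---|---|---|
| W2D1 | 5 (weeks 3-7) | 5 x 2.5 = 12.5 mg | 5 x 7.5 = 37.5 mg |
| W3D1 | 4 (weeks 4-7) | 4 x 2.5 = 10 mg | 4 x 7.5 = 30 mg |

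Two of the three doses in the DLT window are 10 mg injections, so the conflict arises for two of the three.

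**Step 5: the remaining window dose, W1D1.** This dose is 5 mg, so 2.5 mg is truly one level lower. The next planned injection is 10 mg, and one table level below that is 7.5 mg. Both exceed the 5 mg that caused the DLT. Here 8.2 gives the safer instruction, and any correction has to preserve it.

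**The case against.** **Section 8.2 may be a remnant with little reach.** It ties DLT monitoring to the first 3 patients, and section 4.2.2 describes the safety run-in, with its varied doses, in the past tense. This probably explains where the 5 mg and 2.5 mg figures came from, and it may reduce the number of subjects concerned. It does not remove the conflict. The resumption sentence covers any subject with a DLT, and sections 5.2.2.4 and 5.2.2.7 have no first-3-patients limit either.

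**Discretion and oversight.** Resumption is optional, the Principal Investigator is consulted, and adverse events are reviewed weekly (8.7). These lower the risk. But the discretion concerns whether to resume, and nothing says which section prevails on the dose.

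**2.5 mg is simply the more cautious choice.** It may be, and choosing between 2.5 and 7.5 mg is a clinical judgement. The documents still need to give one answer. As they stand, 5.2.2.4, the table and 5.2.2.7 agree with each other, and 8.2 is the outlier.

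**A stronger reading: a contradiction in the Boost Phase.** A reader might infer that 8.2 requires 2.5 mg every 4 weeks in Boost while section 5.2.2 requires 5 mg: "Following resection, during the Boost Phase, the CMP-001 dose is fixed at 5mg injected subcutaneously at the site of the resected tumor". The documents do not support that as a firm contradiction.
- Section 5.2.2 states the planned Boost dose, and its wording need not bar a reduction for toxicity.
- Sections 5.2.2.4 and 5.2.2.7 supply no Boost dose, since their table is limited to Prime. A planned dose alongside one post-DLT rule can coexist.
- The reach of that rule is uncertain. DLTs are defined in Prime only, where dosing is weekly, and keeping the same schedule may mean the schedule in force at the time of the DLT. On the other side, an every-4-week interval occurs only in Boost, which suggests some carry-over was intended.
- A subject with a DLT at W1D1 who then tolerates reduced Prime doses could already meet the first re-escalation condition before Boost, leaving only Sponsor approval.

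This is an ambiguity to clear up.

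**Conclusion.** Wrong as written, for Prime. Section 8.2's resumption dose and its description of the study dose do not match the current regimen. After a DLT on a 10 mg injection, the protocol gives both 2.5 mg and 7.5 mg, a threefold difference per dose, and the accrual-halt trigger in 8.2 inherits the uncertainty. Whether 2.5 mg carries into Boost is unclear but is not shown to conflict with the planned 5 mg.

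The effect is confined to subjects with a DLT in the first 15 days who resume CMP-001. Their number is unknown, as the documents give no DLT rate for this trial. The Prime totals above assume that no dose is missed and that the reduced dose is kept to week 7. The major pathologic response endpoint, the two-stage design, the sample size and the decision rule are unaffected. The finding rests on the current text and the protocol's own table, with no outside figure.

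**What to change.** Amend the wording of section 8.2:

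- For a DLT after a 10 mg intra-tumoral dose, replace 2.5 mg with one level lower per Table 5.2.2.3-1 (7.5 mg), in line with 5.2.2.4 and 5.2.2.7.
- Keep 2.5 mg as the resumption dose only for a DLT after the 5 mg subcutaneous W1D1 dose, and apply it to the next Prime injection, so that no subject resumes above the dose that caused the DLT. Allow return to a higher dose, including 5 mg in Boost, only under the existing 8.2 re-escalation conditions. This also settles the Boost ambiguity for these subjects.
- State the current doses (5 mg subcutaneous; 10 mg intra-tumoral, equal to the ceiling) in place of the 5 mg and 50% statement.

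A one-line cross-reference in 5.2.2.4 to the W1D1 exception would stop that section from sending the same subject to the table.

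The cost is a wording amendment. No extra patients, visits or data are needed.

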#### 5.2.1.2 Nivolumab dose modification

Nivolumab will be withheld for drug-related Grade 4 hematologic toxicities, non-hematological toxicity  $\geq$  Grade 3 including laboratory abnormalities, and severe or life-threatening AEs as per **Table 5.2.1.2-1** below.

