**Table 5.2.1.2-1: Dose Modification Guidelines for Drug-related Adverse Events.**

Toxicity	Hold Treatment For Grade	Timing for Restarting Treatment	Treatment Discontinuation
Diarrhea/Colitis	2-3	Toxicity resolves to Grade 0-1	Toxicity does not resolve within 12 weeks of last dose or inability to reduce corticosteroid to 10 mg or less of prednisone or equivalent per day within 12 weeks
	4	Permanently discontinue	Permanently discontinue
AST, ALT, or Increased Bilirubin	2	Toxicity resolves to Grade 0-1	Toxicity does not resolve within 12 weeks of last dose
	3-4	Permanently discontinue (see exception below) a	Permanently discontinue
Type 1 diabetes mellitus (if new onset) or Hyperglycemia	T1DM or 3-4	Hold nivolumab and CMP-001 for new onset Type 1 diabetes mellitus or Grade 3-4 hyperglycemia associated with evidence of beta cell failure	Resume nivolumab when patients are clinically and metabolically stable
Hypophysitis	2-4	Toxicity resolves to Grade 0-1. Therapy with nivolumab and CMP-001 can be continued while endocrine replacement therapy is instituted	Toxicity does not resolve within 12 weeks of last dose or inability to reduce corticosteroid to 10 mg or less of prednisone or equivalent per day within 12 weeks
Hyperthyroidism	3	Toxicity resolves to Grade 0-1	Toxicity does not resolve within 12 weeks of last dose or inability to reduce corticosteroid to 10 mg or less of prednisone or equivalent per day within 12 weeks
	4	Permanently discontinue	Permanently discontinue
Hypothyroidism		Therapy with nivolumab and CMP-001 can be continued while thyroid replacement therapy is instituted	Therapy with nivolumab can be continued while thyroid replacement therapy is instituted
Infusion Reaction	2 b	Toxicity resolves to Grade 0-1	Permanently discontinue if toxicity develops despite adequate premedication
	3-4	Permanently discontinue	Permanently discontinue
Pneumonitis	2	Toxicity resolves to Grade 0-1	Toxicity does not resolve within 12 weeks of last dose or inability to reduce corticosteroid to 10 mg or less of prednisone or equivalent per day within 12 weeks Permanently discontinue for recurrent Grade 2 pneumonitis
	3-4	Permanently discontinue	Permanently discontinue
Renal Failure or Nephritis	2	Toxicity resolves to Grade 0-1	Toxicity does not resolve within 12 weeks of last dose or inability to reduce corticosteroid to 10 mg or less of prednisone or equivalent per day within 12 weeks

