	3-4	Permanently discontinue	Permanently discontinue
All Other Drug-Related Toxicity c	3 Severe or	Toxicity resolves to Grade 0-1	Toxicity does not resolve within 12 weeks of last dose or inability to reduce corticosteroid to 10 mg or less of prednisone or equivalent per day within 12 weeks. Exceptions may be sought for neuropathy or other AE following discussion with Principle Investigator.
	4	Permanently discontinue	Permanently discontinue

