**Note: Permanently discontinue for any severe or Grade 3 drug-related AE that recurs or any life-threatening event.**

a For patients with liver metastasis who begin treatment with Grade 2 AST or ALT, if AST or ALT increases by greater than or equal to 50% relative to baseline and lasts for at least 1 week then patients should be discontinued.

b If symptoms resolve within one hour of stopping drug infusion, the infusion may be restarted at 50% of the original infusion rate (e.g., from 100 mL/hr to 50 mL/hr). Otherwise dosing will be held until symptoms resolve and the subject should be premedicated for the next scheduled dose.

c Patients with intolerable or persistent Grade 2 drug-related AE may hold study medication at physician discretion. Permanently discontinue study drug for persistent Grade 2 adverse reactions for which treatment with study drug has been held, that do not recover to Grade 0-1 within 12 weeks of the last dose.

In case toxicity does not resolve to Grade 0-1 within 12 weeks after last infusion, trial treatment should be discontinued after consultation with the Sponsor. With investigator and Sponsor agreement, subjects with a laboratory adverse event still at Grade 2 after 12 weeks may continue treatment in the trial only if asymptomatic and controlled. For information on the management of adverse events, see **Section 5.6.1**.

Subjects who experience a recurrence of the same severe or life-threatening event at the same grade or greater with re-challenge of nivolumab should be discontinued from trial treatment.

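### For a DLT after the first nivolumab dose, Section 8.2 lets nivolumab resume at Grade 1 or less even for events, explicitly Grade 4 AST/ALT, for which Table 5.2.1.2-1 ends it; neither rule is given precedence.

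*Combined protocol and SAP*

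**What the plan says.** **Section 8.2 (Safety Monitoring)** lists nine DLT criteria, one of which is "Grade 4 aspartate aminotransferase (AST) and alanine aminotransferase (ALT"). A DLT must be at least possibly related to the CMP-001 plus nivolumab regimen and occur in the first 15 days of the Prime Phase. For any DLT: "Subjects who experience a DLT will have CMP-001 and nivolumab dosing withheld until the toxicity has returned to" Grade 1 or less. CMP-001 may then resume at a reduced dose if the investigator judges that this serves the patient. On nivolumab the section adds only: "Subjects may remain on the same dose of nivolumab. Any dose modification should follow the approved nivolumab label".

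**Section 5.2.1.2 and Table 5.2.1.2-1** give event-specific rules for nivolumab. For drug-related Grade 3-4 AST, ALT or bilirubin the entry is "Permanently discontinue (see exception below"). Permanent discontinuation is also the rule for Grade 4 diarrhea/colitis, Grade 3-4 pneumonitis, Grade 3-4 nephritis, Grade 3-4 infusion reaction and, through the row "All Other Drug-Related Toxicity", any other Grade 4 event. A note below the table adds: "Permanently discontinue for any severe or Grade 3 drug-related AE that recurs or any life-threatening event".

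**Table 5.6.1-1** stops all further trial treatment after a Grade 3 or 4 infusion reaction.

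**The concern.** Section 8.2 is the only place that says what happens to nivolumab after a DLT as such, so an investigator handling one may reasonably treat it as controlling. It sets one end point for the hold, Grade 1 or less, whatever the organ or grade, and sends further questions to the product label, not to the protocol's own table. For some DLTs that table says nivolumab must end.

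What is at stake is patient safety. An investigator who follows Section 8.2 could give nivolumab again after severe hepatic or pulmonary toxicity when another section of the same protocol forbids it. Following either section could be recorded as a deviation from the other. The primary endpoint, the stage boundaries and the error rates are not involved.

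**Working it through.** The plan states no figure on this point, so the check is a comparison of texts followed by simple counts.

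**1. The two rules side by side (DLT attributed to the regimen, patient already exposed to nivolumab)**

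| Event | Section 8.2 | Tables 5.2.1.2-1 and 5.6.1-1 |
|---|---|---|
| Grade 4 AST/ALT (named DLT) | Hold to Grade 1 or less; label | End nivolumab |
| Grade 3-4 pneumonitis | Same | End nivolumab |
| Grade 3-4 infusion reaction | Same | End all trial treatment (Table 5.6.1-1) |
| Grade 3-4 nephritis meeting a DLT criterion | Same | End nivolumab |
| Grade 4 diarrhea despite maximal treatment | Same | End nivolumab |
| Grade 3 diarrhea despite maximal treatment | Same | Hold, may restart: **no clash** |
| Grade 4 neutropenia or thrombocytopenia | Same | Catch-all row ends it; Section 5.2.1.2 text says withheld: **unclear** |

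**2. Does the table's exception for AST/ALT resolve it?** No. The footnote concerns patients with liver metastasis who start with Grade 2 AST or ALT. Section 5.1.2 requires M0, and Section 5.2.2.3 rules out patients with visceral tumors.

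**3. Does any passage set precedence?**
- Section 5.2.1.2 introduces the table without mentioning DLTs.
- Section 5.6.1 sends readers to Section 5.2.1 for dose modification, within supportive-care guidance.
- The footnote to Table 7.2.2.4-1 cites Section 5.2.1 for dose reductions due to DLTs.
- Section 5.2.2.7 gives a DLT rule for CMP-001 only.
- Section 5.2.2.4 resumes the combination after a CMP-001-related DLT with no condition on nivolumab.

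Two of these point toward Section 5.2.1. None says that it overrides Section 8.2.

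**4. How the nine criteria divide.** There are 5 hematologic and 4 non-hematologic criteria (5 + 4 = 9).
- Explicit match to a discontinuation row: 1 (Grade 4 AST/ALT).
- Match depending on grade or organ: 3 (the other non-hematologic criteria; the laboratory one through, for example, Grade 3-4 bilirubin leading to an overnight stay).
- Catch-all row or table note only: 5 (all hematologic), of which 2 are Grade 4 by definition.
- Check: 1 + 3 + 5 = 9.

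**5. Which part of the DLT window is affected.** Day 1 of week k is study day 7(k − 1) + 1. Week 2 day 1 is therefore day 8, week 3 day 1 is day 15 and week 4 day 1 is day 22. Section 5.2.1.4 gives Prime Phase nivolumab on day 1 of weeks 2, 4 and 6. On exact schedule, days 1 to 7 of the 15-day window precede any nivolumab, and a clash can arise only from day 8 to day 15.

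**6. Doses that depend on the decision.** Planned nivolumab doses are 3 Prime + 12 Boost = 15 (every 4 weeks) or 3 + 23 = 26 (every 2 weeks). One dose falls inside the window, leaving 15 − 1 = **14 of 15**, or 26 − 1 = **25 of 26**. Section 8.2 also says "we will monitor dose limiting toxicities (DLTs) for 4 weeks". If the rule were applied over those 28 days, the day 22 dose could also have been given, leaving at least 15 − 2 = 13 of 15 or 26 − 2 = 24 of 26.

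**7. Patients in scope.** DLT monitoring is stated for the first 3 patients, but the hold rule speaks of subjects with a DLT without limit. The range runs from 3 to the 33 planned in Section 8.3. Section 5.2 allows up to 40 evaluable, which would raise the upper end.

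**The case against.** The best defense is that the two rules can be read together. Section 8.2 never orders a nivolumab restart: its only resumption sentence concerns CMP-001, and the sentence on keeping the nivolumab dose can mean just that the dose is not reduced. The protocol also uses the word for holding loosely. Section 5.2.1.2 opens with "Nivolumab will be withheld for drug-related Grade 4 hematologic toxicities", yet points to a table that contains permanent stops. The cross-references in Section 5.6.1 and Table 7.2.2.4-1 lead to Section 5.2.1, which has no nivolumab dose-reduction levels, so they can only mean its hold and stop rules. Many readers would take the stricter, event-specific instruction. And if the label also requires stopping, practice would agree with the table.

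Much of this stands. It shows a permissive gap, not a contrary order. It does not close the gap: Section 5.2.1.2 ties its hold to the table, whereas Section 8.2 cites no table and sets its own end point. The label is not in the documents, so its effect cannot be assumed either way.

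A reader might also infer that every Grade 4 AST/ALT DLT produces a clash. The documents do not support that. A DLT in days 1 to 7 precedes nivolumab on schedule, and waiting for recovery before a first dose is sensible. Sections 5.2.2.4 and 5.7 also recognize toxicity due to CMP-001; under Section 5.7, nivolumab may continue if it is not implicated.

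Finally, Section 4.2.2 describes the safety run-in in the past tense, so monitoring of the first 3 patients may already be over. If the DLT rule ends with them, the conflict no longer affects new patients.

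**Conclusion.** The inconsistency is real but narrow. For a regimen-attributed DLT after the first nivolumab dose, Section 8.2 permits resumption at Grade 1 or less with no exception for events that the protocol's tables list as ending nivolumab. Grade 4 AST/ALT is the one explicit clash. Grade 3-4 pneumonitis, Grade 3-4 infusion reaction, qualifying Grade 3-4 nephritis and Grade 4 diarrhea can clash depending on the event. Grade 4 hematologic events are ambiguous within Section 5.2.1.2 itself and should not be counted as a plain contradiction.

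The conclusion assumes attribution to the combination, as Sections 7.2.2.2 and 8.2 direct, and dosing on schedule. The number of patients affected is unknown: no event rate can be derived, and the reach of the rule beyond the first 3 patients is unclear. For an affected patient nearly all planned nivolumab depends on which section is followed. It should be corrected as a safety clarification. It gives no reason to change the sample size or the two-stage boundaries.

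**What to change.** In Section 8.2, replace the two sentences on nivolumab dose and label with wording such as:

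> *After a DLT in a subject who has received nivolumab, nivolumab is managed by Table 5.2.1.2-1 (and Table 5.6.1-1 for infusion reactions), which prevail over this section. It may resume, without dose reduction, at Grade 1 or less only for events these tables allow to restart; events listed as permanently discontinue end nivolumab. Where Table 5.6.1-1 or Section 5.7 requires stopping all trial treatment, CMP-001 also stops. For a DLT before the first nivolumab dose, nivolumab may start once the event is Grade 1 or less, after consultation with the Principal Investigator. The approved label applies to matters the tables do not cover.*

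Make resumption of the combination in Section 5.2.2.4 subject to the same rule. Add a row to Table 5.2.1.2-1 stating whether Grade 4 hematologic events are held or stopped.

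The cost is wording in two places and one table row. The label keeps a role, but a smaller one. A few patients lose the option of nivolumab re-challenge. The separate sentence for DLTs before exposure is needed, because otherwise a patient who had never received nivolumab could be barred from it.
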